APPENDIX D: EVRL PROPER USE REFERENCE GUIDE

APPENDIX K: NEUROPATHIC PAIN SYMPTOM INVENTORY (NPSI)

APPENDIX L: RESEARCH SUBJECT INFORMATION AND CONSENT FORM

APPENDIX M: CASE REPORT FORMS

STUDY INFORMATION

SPONSOR

Erchonia Corporation
[name]
[name]
Contact: [name]
[contact] ext. 7510
E-mail: [contact]
www.erchonia.com

REGULATORY AND CLINICAL CONSULTANT

[name]
[name]
Contact: [name], BS, MS, EMT-P
Principal Consultant
[contact]
E-mail: [contact]

MONITOR

Erchonia Corporation
[name]
[name]
Contact: [name]
[contact] ext. 7510
E-mail: [contact]
www.erchonia.com

PRINCIPAL CLINICAL INVESTIGATORS AND TEST SITES

Test Site #1: [name], DPM
[name]
[name]
[contact]
E-mail: [contact]

Test Site #2: [name], DPM
Franco & Co Podiatry MedSpa
[name]
[name]
[contact]
E-mail: [contact]

Test Site #3: [name]
[name] Center for Age and Weight Management
[name]
[name]
[contact]
E-mail: [contact]

Test Site #4: [name], DC
Laser Chiropractic
[name]
[name]
[contact]
E-mail: [contact]

INSTITUTIONAL REVIEW BOARD

WIRB Copernicus Group (WCG)
[name]
[name]
[contact]
IRB Tracking Number: 20220447
E-mail: [contact]
www.wcgclinical.com

PURPOSE OF STUDY

The purpose of this clinical study is to determine the effectiveness of the Erchonia® EVRL, manufactured by Erchonia Corporation (the Company), in providing prescription home use application for temporary relief of diabetic neuropathy foot pain in individuals diagnosed with diabetic neuropathy by a suitably qualified and licensed health professional.

EXPECTED RESULTS

Following completion of the study treatment administration protocol with the Erchonia® EVRL, it is anticipated that compared to baseline, at least 35% more subjects in the test group than in the placebo group will show a 30% or greater reduction in self-reported VAS pain rating in the feet at study endpoint evaluation relative to baseline.

STUDY DESIGN

This clinical study is a prospective, double blind, placebo-controlled, randomized design evaluation of the effect of the Erchonia® EVRL for prescription home use application in providing temporary relief of diabetic neuropathy foot pain.

SUBJECT GROUPS

Subjects enrolled in the clinical study will not have been enrolled in the Human Factors Validation Testing study.

Each enrolled subject will be randomized to the active treatment group or to the placebo treatment group of the clinical study, as follows:

Active treatment group: Subjects randomized to the active treatment group will self-administer the study treatments with the active (true) Erchonia® EVRL laser in his or her own home.

Placebo treatment group: Subjects randomized to the placebo treatment group will self-administer the study procedures with a 'fake' (placebo) Erchonia® EVRL laser in his or her own home. The 'fake' (placebo) laser device will appear to the subject to be an active device but will not produce any therapeutic light output. The placebo laser device is designed to have the same physical appearance as the actual (active) laser device, including the appearance of any visible and invisible light output. Therefore, both the active and placebo devices emit light when activated that is indistinguishable to the subject. As the laser light does not put out any notable degree of heat or noise, these are also not distinguishing factors for subjects between the active and placebo devices.

Regardless of whether the subject self-administers the study treatments with the actual or the fake laser device, all subjects will be required to adhere to all phases of the entire protocol design.

DOUBLE BLIND DESIGN

This clinical study is a double-blind design, such that neither the subject nor the investigator is aware of whether the subject has been provided with the active or the placebo Erchonia® EVRL device. Unblinding will occur after the final data set has been fully analyzed.

The blinding procedure is as follows:

- 1) Each subject is randomly assigned to Treatment Group A or to Treatment Group B. Subjects assigned to Treatment Group A will receive the Erchonia® EVRL A and subjects assigned to Treatment Group B will receive the Erchonia® EVRL B. Only one individual employee at the study Sponsor site will know which label ('A' or 'B') corresponds to the actual (active) EVRL device and which label corresponds to the 'fake' device until the final study data set analysis is complete. That individual will ensure that this information is stored and maintained confidentially at the Sponsor's work site.
- 2) The fake (placebo) Erchonia® EVRL is designed to have the same physical appearance as the actual Erchonia® EVRL, including the appearance of any visible and invisible light output. Therefore, both the test and placebo devices emit light when activated that is indistinguishable to both the subject and to the investigator. As the laser light does not put out any notable degree of heat or noise, these are not distinguishing factors for subjects between the two groups.

RANDOMIZATION

Subject randomization occurs following attainment of subject consent. Subject allocation to treatment group will be via variable block randomization with varying block sizes of two, four and six used at random to minimize the likelihood of predicting the next treatment group assignment.

Randomization will be attained using computer generation sequence methodology, ensuring that the randomization methodology and the generated allocation sequence is concealed from the subjects.

Concealment will be insured as follows:

- (ii) Each computer-generated randomization sequence is unique and will therefore not be able to be replicated.
- (iii) Randomization will occur to either 'Treatment Group A' or to 'Treatment Group B' rather than to a test or placebo group, and only one designated individual at the Sponsor site will know which assignment (A or B) corresponds to the active device and which corresponds to the fake device. Unblinding will not occur until the final study data set analysis is complete.

SUBJECTS

Recruitment

Subjects will be recruited from online advertisements for individuals who have been previously diagnosed with diabetes induced peripheral neuropathy by a suitably qualified and licensed health professional.

Compensation

A subject who completes his or her participation in this clinical study through to the final post-treatment administration will receive financial compensation of \$200.

A subject will not be charged for the cost of the study treatments with the Erchonia® EVRL Laser or for the cost of any other directly-related evaluations or measurements that occur as part of his or her participation in the study.

Sample size

There will be 64 qualified subjects enrolled in this clinical study:

32 subjects in the active treatment group
32 subjects in the po treatment group

Rationale for sample size

Based on the following parameters established for the purposes of assessing efficacy of the Erchonia® EVRL in this clinical study ...:

- Individual subject success criteria defined as a 30% or greater reduction in self-reported Degree of Pain rating on the 0-100 VAS from baseline to study endpoint evaluation.

N.B.: The clinical relevance of a 30% change in VAS score is explained and supported in the STATISTICAL ANALYSIS PLAN section further along in this protocol document.

- Overall study success criteria of at least a 35% difference between the active device group and the placebo device group, comparing the proportion of individual successes in each group.
- It is anticipated that about 55% of subjects in the active device group and about 20% of subjects in the placebo device group will meet the individual success criteria, and
- intended application of a two-tailed test with an alpha value of 0.05 and Power of 0.8

...the sample size of 29 subjects per group (active group and placebo group, separately) has been determined using the following reference calculator: *Hypothesis Testing: Categorical Data - Estimation of Sample Size and Power for Comparing Two Binomial Proportions* in Bernard Rosner's *Fundamentals of Biostatistics*.

For the purposes of sample size calculation, it is anticipated that about one-twentieth of subjects overall may withdraw from the study prior to completion for various reasons. Therefore, the following formula is used to determine the final needed starting sample size for each group:

Final sample size = sample size X 1/(1-d); where d = # expected dropouts/# subjects enrolled.

Final sample size = 29 X 1/(1-0.083)

Final sample size = 29 X 1/0.917 = 29 X 1.0905 = 31.62, rounded to 32 subjects per treatment group.

Therefore, a minimum starting sample size of 32 subjects in each treatment group is needed to ensure that sufficient numbers remains at the end of the trial (29 subjects per group) for any significant differences found between groups to be considered statistically valid and representative of the general population being sampled. This results in a total of 64 subjects being enrolled in this study across both study treatment groups.

STUDY PROCEDURE

STUDY TEST BATTERY

The following are the study assessment tools to be used and the variables to be recorded in this clinical study.

BASELINE VARIABLES

A. Neuropathy Variables

- Number of months/years since onset of foot pain.
- Number of months/years since diabetes diagnosis
- Insulin dependency

B. Medication and Treatment

- *Current medication for diabetic peripheral neuropathy foot pain:* Record all medications currently used for the management of neuropathy pain symptoms.
- *Prior treatment approaches for diabetic peripheral neuropathy foot pain:* Record all prior treatments, whether conventional or alternative.
- *Concomitant Medication and Therapy Use:* Record all over-the-counter and prescription medications currently used for any indication (other than the management of neuropathy pain symptoms)

C. Subject Demographics: Subject age, gender and ethnicity are recorded.

OUTCOME ASSESSMENT TOOLS

PRIMARY OUTCOME MEASURE:

VISUAL ANALOG SCALE (VAS) DEGREE OF PAIN RATING: Subjects will be asked to rate the overall degree of pain experienced in their feet on the following 0-100 mm (0 -10 cm) Visual Analog Pain Scale, by responding to the following question:

“Using the scale below, please mark with a cross (X) the spot along the 0 to 100 line below that best shows **how much pain you feel in your feet** right now. ‘0’ means you feel no pain at all and ‘100’ means you feel the worst pain imaginable. **Please mark only one spot. Do not think of or write in a number.**”

The Visual Analog Pain Scale (VAS) is one of the three most commonly used scales for assessing chronic pain. It is a simple scale that consists of a line anchored at one end by a label such as "NO PAIN" and at the other end "WORST POSSIBLE PAIN". The subject marks on the line the spot for the pain intensity, which is then measured.

Like a thermometer, this means that its two ends are rooted, and a doubling of the score does accurately reflect a doubling of the pain. Consequently, sensitive t-tests and ANOVA methods can

be used in the analysis, so that significant differences can be identified with relatively small sample sizes or small differences between groups.

Source: Measuring Pain by Adrian White, *Acupuncture in Medicine*, November 1998 – Vol 16 No. 2

To participate in the study the subject agrees to refrain from consuming any pain relief medication within 6 hours of recording a required VAS Degree of Pain Rating to ensure that the effect of the pain relief medication does not influence any potential treatment effect of the study treatment with the Erchonia® EVRL as evidenced through the VAS ratings.

SECONDARY OUTCOME MEASURES

NEUROPATHIC PAIN SYMPTOM INVENTORY (NPSI): The NPSI was developed in 2004 by Bouhassira Didier to evaluate the different symptoms of neuropathic pain in adults. It is a 12-item self-administered patient-reported outcome (PRO) assessment tool with a recall/ observation period of over the past 24 hours. It contains 10 descriptors representing 5 distinct dimensions on the basis of factor analysis: burning pain, deep pain, paroxysmal pain, evoked pain, paresthesia/dysesthesia, and 2 temporal items designed to assess pain duration and the number of pain paroxysms. The NPSI has been validated in patients with definite neuropathic pain of peripheral or central origin.

The development and validation of the NPSI is contained in the abstract below:

Development and validation of the Neuropathic Pain Symptom Inventory.

Bouhassira D, Attal N, Fermanian J, Alchaar H, Gautron M, Masquelier E, Rostaing S, Lanteri-Minet M, Collin E, Grisart J, Boureau F.

Pain. 2004 Apr;108(3):248-57.

This study describes the development and validation of the Neuropathic Pain Symptom Inventory (NPSI), a new self-questionnaire specifically designed to evaluate the different symptoms of neuropathic pain. Following a development phase and a pilot study, we generated a list of descriptors reflecting spontaneous ongoing or paroxysmal pain, evoked pain (i.e. mechanical and thermal allodynia/hyperalgesia) and dysesthesia/paresthesia. Each of these items was quantified on a (0-10) numerical scale. The validation procedure was performed in 176 consecutive patients with neuropathic pain of peripheral (n = 120) or central (n = 56) origin, recruited in five pain centers in France and Belgium. It included: (i) assessment of the test-retest reliability of each item, (ii) determination of the factorial structure of the questionnaire and analysis of convergent and divergent validities (i.e. construct validity), and (iii) evaluation of the ability of the NPSI to detect the effects of treatment (i.e. sensitivity to change). The final version of the NPSI includes 10 descriptors (plus two temporal items) that allow discrimination and quantification of five distinct clinically relevant dimensions of neuropathic pain syndromes and that are sensitive to treatment. The psychometric properties of the NPSI suggest that it might be used to characterize subgroups of neuropathic pain patients and verify whether they respond differentially to various pharmacological agents or other therapeutic interventions.

PMID: 15030944

The full article and the NPSI Assessment tool are contained in **Appendix K** of this clinical study protocol.

Subject Satisfaction With Study Outcome

The subject is asked to rate how satisfied he or she is with any change in his or her overall foot pain following completion of the laser administration procedures with the Erchonia® EVRL by using the 5-point Likert scale presented below to respond to the following question: "Overall, how satisfied or dissatisfied are you with any change in your foot pain following the study procedures with the study laser device?"

- Very Satisfied
- Somewhat Satisfied
- Neither Satisfied nor Dissatisfied
- Not Very Satisfied
- Not at All Satisfied

BLINDING EFFICACY EVALUATION TOOLS

Subject Perceived Group Allocation and Rationale

The subject records whether he or she believes to have received the study treatments with the true or fake Erchonia® EVRL and records verbatim his or her reasoning or rationale for this perceived determination.

STUDY PROCEDURE PROTOCOL

STUDY QUALIFICATION

SIGNING OF INFORMED CONSENT FORM

The investigator will commence by presenting and reviewing in detail the items in the informed consent form with the individual and answer any questions. To proceed, the individual must willingly sign the informed consent form.

ASSIGNMENT OF SUBJECT IDENTIFICATION NUMBER

The subject is assigned to a unique subject identification number based upon his or her order of entry into the study.

Additional information about the informed consent and subject ID number assignment is contained in a later section of the protocol titled, "SAFETY AND CONFIDENTIALITY ISSUES."

SUBJECT RANDOMIZATION TO TREATMENT GROUP

Following signing of the consent form and prior to study qualification evaluation, a subject is randomly assigned to Treatment Group A or to Treatment Group B, following the methodology outlined above in the STUDY DESIGN section of the protocol.

STUDY QUALIFICATION CHECKLIST

To be eligible for study participation, a subject must satisfy the following qualification criteria:

INCLUSION CRITERIA

To be eligible for study participation, a subject must satisfy each of the following criteria.

- Previously diagnosed with diabetes induced peripheral neuropathy by a suitably qualified and licensed health professional within the past 6 months.

- Over the age of 18 years.
- Able to read and write English.
- Constant feet pain on-going over at least the past 3 months.
- If using analgesics (pain medication), must be on a stable analgesic regimen (i.e., no changes to the prescribed analgesic regimen) over a period of at least 14 days prior to enrollment; and willing and able to not have planned upward dose titration of analgesics during the study period. The subject may elect to decrease analgesic use during the study. Cannabis prescribed for medicinal purposes would qualify as an analgesic in this context.
- Willing and able to refrain from engaging in any non-study procedure therapies for the management of foot pain throughout the course of study participation, including conventional therapies such as physical therapy, occupational therapy and hot or cold packs, as well as alternative therapies such as chiropractic care and acupuncture.
- Agrees to refrain from taking a dosage of analgesic (pain medication) for at least 6 hours before a scheduled VAS foot pain rating is to be recorded.
- Subjects' degree of foot pain on the 0-100 VAS, with "0" being no pain and "100" being worst pain imaginable, is 50 or greater.

EXCLUSION CRITERIA

A subject who satisfies any of the following criteria will be excluded from study participation:

- Pregnant or think they might be pregnant.
- Open wounds (sores, cuts, ulcers, etc.) around the feet
- Cancerous growths around the feet.
- Difficulty with hand dexterity sufficient to impact ability to administer treatments with the laser such as from severe arthritis in the hands, Multiple Sclerosis, Cerebral Palsy, Parkinson's Disease, Huntington's Disease, etc.

PRE-TREATMENT EVALUATION PHASE

The pre-treatment evaluation phase commences following successful study qualification.

BASELINE VARIABLES

- Baseline Foot Variables
- Medication and Treatment
- Insulin Dependency
- Subject Demographics

PRE-TREATMENT OUTCOME ASSESSMENTS

- Visual Analog Scale (VAS) Degree of Foot Pain Rating
- Neuropathic Pain Symptom Inventory (NPSI)

The Pre-Treatment Outcome assessments will serve as the Baseline data set.

AT-HOME TREATMENT ADMINISTRATION PHASE

A fully qualified enrolled subject will be provided either a Erchonia® EVRL A or B device based on his or her randomization to treatment group (see Randomization). Additionally, the enrolled subject will be provided the EVRL Proper Use Reference Guide (**Appendix D**) and applicable Case Report Forms (**Appendix M**) for capturing study outcome assessments.

TREATMENT ADMINISTRATION PROTOCOL

- The treatment administration phase extends over 3 consecutive weeks.
- The subject self-administers two treatment administrations with the Erchonia® EVRL (A or B) on each consecutive day of the 3-week treatment administration phase for a total of 42 self-administered treatments.
- Each treatment administration lasts 5 minutes per foot, for a total of 10 minutes.
- Each treatment is self-administered by the subject in his or her own home.

TREATMENT ADMINISTRATION PHASE MEASURES

The following treatment administration phase measures will be recorded by the subject at home through the provided Case Report Forms (**Appendix M**).

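### Two shared device codes (A and B) make every allocation knowable once one letter is unmasked; individual kit numbers would limit this to one subject

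*Combined protocol and SAP*

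**What the plan says.** The Double Blind Design section assigns each subject to Group A or Group B and ties the device to the group: "Subjects assigned to Treatment Group A will receive the Erchonia® EVRL A", and Group B receives the other device. The key is closely held: "Only one individual employee at the study Sponsor site will know which label ('A' or 'B') corresponds to the actual (active) EVRL device", and unblinding waits until the final analysis is complete.

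The Randomization section offers the letters as a concealment measure: "Randomization will occur to either 'Treatment Group A' or to 'Treatment Group B' rather than to a test or placebo group". It also specifies "varying block sizes of two, four and six used at random to minimize the likelihood of predicting the next treatment group assignment". It says the sequence is concealed from subjects and does not mention site staff. It does not say whether there is one central list or one per site, or who holds it.

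Under Subject Randomization to Treatment Group, the letter is assigned after consent and before the qualification evaluation, which includes a VAS of at least 50. Under At-Home Treatment Administration Phase, the subject "will be provided either a Erchonia® EVRL A or B device based on his or her randomization to treatment group". No kit or device number is described anywhere. Under Individual Test Site Data, there are four sites.

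**The concern.** The letters hide the arm only while nobody outside the key-holder knows what either letter means. Because each letter has one meaning for every subject at every site, the blind has a single point of failure. The primary outcome is a subjective self-rating recorded at home, so the credibility of the result depends heavily on blinding.

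There are two routes to that failure. One is an unmasking of a single device. The plan itself allows for this: its Blinding Efficacy Evaluation lists sensory or visual clues and overheard staff conversations as signs that blinding has failed. The other is inference from results. If outcomes can be seen beside letters, the better-performing letter suggests itself as active and no code break is needed.

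Two consequences follow. Because the letter is assigned before qualification, staff who learn it then, and who know or believe they know which letter is active, could be influenced at the eligibility decision. Visible letters also give anyone following the blocks some information about the next assignment.

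**Working it through.** The plan gives no figure for blinding risk, so there is none to reproduce. The response rates used below are those of the sample-size section; they do reproduce its 29 per group (two-sided 5%, uncorrected normal approximation, power 80.2%).

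**1. Exposure from one unmasking.** Inputs: 2 codes, 64 subjects, fixed mapping (Double Blind Design; Sample size).
- Two shared codes: learning one letter fixes the other, so 64 of 64 allocations become knowable to anyone who sees the letters.
- One code per device: 1 of 64.

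This step needs no assumed probability.

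**2. Inference from outcomes by letter.** Inputs: response rates 55% active and 20% placebo (Rationale for sample size). Assumption: equal sites and an even split, so 64/4 = 16 subjects per site and 8 per letter. Let X ~ Binomial(n, 0.55) and Y ~ Binomial(n, 0.20), independent; the quantity is P(X > Y).

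| Subjects per letter | Active letter ahead | Tie | Placebo letter ahead |
|---|---|---|---|
| 8 | 89.7% | 6.6% | 3.7% |
| 16 | 97.5% | 1.5% | 1.0% |

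This holds only if the anticipated effect is real and someone sees outcomes beside letters. The Privacy and Confidentiality section keeps original records at the sites and sends copies of all case report forms to the statistician and the sponsor, which is also listed as monitor. The documents do not say that the letter appears on those forms. They also describe nothing that keeps letters and outcomes apart.

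**3. Guessing the next letter.** Inputs: block sizes "variable block randomization with varying block sizes of two, four and six used at random to minimize the likelihood of predicting". Assumption: the three sizes are equally likely. After the first letter of a known fresh block, the opposite letter has probability (1/1 + 2/3 + 3/5)/3 = 75.6%. Over a whole list, the rule is to guess the letter that is behind and toss a coin when level. Simulated results:

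| What the guesser sees | Correct guesses |
|---|---|
| Full sequence, one list of 64 | 70.1% |
| Full sequence, separate site lists of 16 | 69.5% |
| Own site's part of one central list (4 sites, subjects arriving at random) | 52.2% |
| Chance | 50% |

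Even with the full sequence of 64 visible, only about 4% of assignments can be predicted with certainty.

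**The case against.** Several counter-arguments have force.

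- **Prediction.** A reader might infer that staff can predict upcoming assignments and that the varying blocks are defeated. The documents do not support that. They do not say what staff see; in the least favourable case certainty is rare, and in the most favourable case examined guessing is close to chance. A predicted letter is also not a predicted arm: it biases selection only once someone knows or believes which letter is active. At the eligibility decision prediction is beside the point, because the letter has already been assigned. That part of the risk comes jointly from the timing of randomisation and the shared letter.
- **A probability that the whole trial is unblinded.** One could assume a 1% unmasking risk per device and compute 1 − 0.99^64 = 47% (27% at 0.5%, 73% at 2%). Nothing in the documents anchors that risk. The formula also treats knowable allocations as known to all. Subjects treat and rate themselves at home; one subject working out a device does not inform 63 others, and ratings already recorded cannot be affected.
- **Existing safeguards.** The plan says the active and placebo devices are indistinguishable to subject and investigator, restricts the key to one employee, plans no code break before the final analysis, and collects perceived allocation at Weeks 3 and 7. These lower the chance of a failure or help to detect one. They do not limit how far a failure spreads.
- **Limits of the text.** That the letter is visible is implied by calling it a label and naming the issued device by letter, but it is not stated outright. The concealment list as available starts at item (ii), so an item on who holds the sequence may have been lost in extraction. The case report forms are not shown.

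What survives is the structural point: two codes, one fixed meaning each, and no individual device codes described.

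**Conclusion.** The concern holds in a limited form. With two shared codes, one reliable unmasking of either letter, or outcomes pooled by letter, makes all 64 allocations knowable to anyone who sees the letters, against one subject with individual codes. That conclusion rests only on the fixed mapping and on the letters being visible, which is the natural reading.

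The figure of about 90% for inferring the active letter at 8 per letter further assumes equal sites, the plan's own effect size, and access to outcomes beside letters. The effect on block concealment lies between about 52% and 70% correct guesses according to what staff see, which the plan leaves open. The documents do not show that the blind has been or will be broken, nor that selection is biased. This is an avoidable weakness that should be corrected; it does not by itself invalidate the design.

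**What to change.** Give each device its own kit number and have the randomisation list assign kit numbers. Keep the kit-to-arm list only with the designated sponsor employee. Show no A/B letter on devices, site records or case report forms. Give the statistician masked arm codes only for the final analysis. State in the Randomization section whether the list is central or per site, and that it is concealed from site staff as well as subjects.

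The cost is relabelling the devices and keeping one kit list. Sample size, treatment and analysis are unchanged.

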Based on over twenty-five (25) years of experience conducting comparable clinical trials through the study Sponsor, Erchonia Corporation, the relatively small sample size, the short duration of the trial, and the minimal requirements and commitments required from enrolled subjects, it is anticipated that withdrawal and lost-to-follow-up rates will be minimal and so will be missing data. Therefore, the single imputation methodology is selected as that to be implemented to account for any missing data. Single imputation methodology is applicable to impute missing values when a dataset is small, the number of missing values is small, the missing data is assumed to be Missing Completely at Random (MCAR), and outcome analysis procedures are simple. The single imputation methodology selected for this study is whichever is more conservative of the mean or the median of the variable for the treatment group from which the missing data emanated.

BASELINE RECORDINGS

SAMPLE DEMOGRAPHICS

Sample demographics recorded at Baseline assessment will be summarized descriptively by treatment group, using mean, standard deviation, median and range (minimum, maximum) for the continuous variable of subject age in years, and by number (N) and percentage (%) for the categorical sample variables of gender and ethnicity. Sample demographics will be compared for differences between treatment groups and test sites. Any identified differences will be explored with respect to potential impact on study outcome.

NEUROPATHY VARIABLES

Sample neuropathy continuous variables recorded at Baseline assessment of months since diagnosis of diabetes, and months since onset of peripheral neuropathy foot pain will be summarized descriptively by treatment group, using mean, standard deviation, median and range (minimum, maximum). The categorical Baseline neuropathy variable of presence or absence of insulin dependency will be summarized descriptively by number (N) and percentage (%) per category. Sample demographics will be compared for differences between treatment groups and test sites. Any identified differences will be explored with respect to potential impact on study outcome.

MEDICATION AND TREATMENT

The below medication and treatment usage as recorded at Baseline assessment will be summarized categorically by, and compared between, treatment groups using number (N) and percentage (%):

- (i) Current medications taken for relief of diabetic foot pain

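### Does giving the withdrawal rate as one-twentieth in words but 0.083 in the formula undermine the sample size of 64?

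*Combined protocol and SAP*

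**What the plan says.** Everything relevant to the size of the trial is in the combined protocol and SAP, section SUBJECTS, under Sample size and Rationale for sample size.

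- Planning rates: "about 55% of subjects in the active device group and about 20% of subjects in the placebo device group will meet the individual success criteria".
- Test: "intended application of a two-tailed test with an alpha value of 0.05 and Power of 0.8".
- Result before allowing for withdrawal: "the sample size of 29 subjects per group (active group and placebo group, separately) has been determined".
- Withdrawal in words: "it is anticipated that about one-twentieth of subjects overall may withdraw from the study prior to completion for various reasons".
- Withdrawal in the calculation, where d is defined as expected dropouts divided by subjects enrolled: "Final sample size = 29 X 1/(1-0.083", carried on to 0.917, 1.0905, 31.62 and then 32.
- Conclusion of the paragraph: "a minimum starting sample size of 32 subjects in each treatment group is needed".
- Enrolment: "There will be 64 qualified subjects enrolled in this clinical study", split 32 and 32.

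The only other remark on withdrawal is under HANDLING OF MISSING DATA in the STATISTICAL ANALYSIS section, where "it is anticipated that withdrawal and lost-to-follow-up rates will be minimal". It gives no figure and is compatible with either rate.

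**The concern.** The sentence in words leads straight into the formula as its justification, and d is defined as the proportion of enrolled subjects expected to drop out. The two values therefore describe the same thing, yet one-twentieth is 0.05 and the formula has 0.083, close to one-twelfth. The word *about* does not bridge the gap, because 8.3% is two-thirds higher than 5%. The word *overall* does not either, because the groups are equal in size and one d is applied to both.

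A sample size should be derivable from its stated inputs. Of the two stated rates, only 0.083 gives the 32 per group that the text calls the minimum. A reader who takes the words at face value gets 31 and cannot tell whether the 32nd subject in each group is required or spare. Had the slip gone the other way, with a higher rate in words than in the formula, the trial could have been planned too small for its own assumptions. That possibility is why the point needed checking.

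**Working it through.** **Inputs** (all from Rationale for sample size): responder rates 0.55 and 0.20, two-sided alpha 0.05, power 0.80, equal groups, d = 0.05 in words and d = 0.083 in the formula.

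**1. Reproduce the base size.** Two-proportion formula with pooled variance under the null and no continuity correction:

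n = [1.960 × √(2 × 0.375 × 0.625) + 0.8416 × √(0.55 × 0.45 + 0.20 × 0.80)]² / 0.35²

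= (1.3419 + 0.5373)² / 0.1225 = 28.83, rounded up to 29 per group.

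This is the plan's figure, so any fault is confined to the withdrawal step.

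**2. Apply the plan's inflation, 29/(1 − d), at each rate.**

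| d | 29/(1 − d) | Per group | Total |
|---|---|---|---|
| 0.05 | 29/0.95 = 30.53 | 31 | 62 |
| 0.083 | 29/0.917 = 31.62 | 32 | 64 |

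The second row reproduces the plan's 31.62, 32 and 64.

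**3. Which rates give 32?** Rounding up gives 32 when 29/(1 − d) is above 31 and at most 32. That means d above 1 − 29/31 = 6.45% and up to 1 − 29/32 = 9.375%. The formula's 8.3% lies in this range and 5% does not, so rounding does not explain the discrepancy.

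**4. Does 64 cover both rates?** Expected completers per group with 32 enrolled:

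- at 5%: 32 × 0.95 = 30.4
- at 8.3%: 32 × 0.917 = 29.3

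Both exceed 29.

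**5. Power of the test of equal proportions at the planning rates.** By the same normal approximation it is 80.2% with 29 per group and 84.1% with 32. Completers at either rate fall between these two sizes, so the nominal 80% is met on expectation. These are approximations: exact enumeration of the uncorrected chi-squared test at 29 per group gives 79.6%. That small gap belongs to the base-size formula and has nothing to do with the withdrawal rate.

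**6. Does the rate enter the analysis?** Under STUDY ANALYSIS POPULATIONS, the principal population is all consented and enrolled subjects, and HANDLING OF MISSING DATA fills gaps by single imputation. Subjects who withdraw therefore remain in the principal comparison at either rate. The allowance bears on the number of completers, which matters for the supporting per-protocol analysis.

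**The case for a change.** The best case for asking for a correction is that withdrawal is a declared design input and, as printed, the stated minimum cannot be obtained from the rate given in words. The choice also affects how much room the design has. If 31 per group had been enrolled, expected completers would be 31 × 0.95 = 29.5 at 5%, but 31 × 0.917 = 28.4 at 8.3%, below the plan's own target. Changing one phrase or one number would cost almost nothing.

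The inconsistency itself stands. It is in current, legible text, and it is neither a rounding effect nor superseded wording. The claimed stake does not stand. The trial does not enrol 31 per group. It enrols 32, which is sufficient at both rates. The calculation is printed step by step, and 0.083, 31.62, 32 and 64 agree with each other and with the enrolment statement. Only the phrase in words is out of line. That does not prove which rate the sponsor meant, and the basis for 0.083 is not given, but the enrolment figure can be traced without that knowledge. A tidier sentence would leave the conduct and reading of the trial as they are.

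**Conclusion.** The two rates do disagree, but the disagreement is clerical and no change to the plan follows. It amounts to one subject per group, two in total, and the plan already enrols the larger number. The figures the trial relies on (29 completers per group, 32 enrolled per group, 64 in total, a nominal 80% power for the test of equal proportions) hold whichever rate was intended.

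This rests on three assumptions: the responder rates of 55% and 20%, withdrawal that is similar in the two groups, and actual withdrawal no higher than 9.375%, the most that 32 per group can lose on expectation while keeping 29.

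The conclusion is limited to the withdrawal allowance. It does not assess the separate criterion, under PRIMARY EFFICACY OUTCOME MEASURE, that the observed difference reach 35 percentage points. The power figures above concern only the test of equal proportions and should not be read as covering that criterion.
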